**Patch Test Site Assessments:**

Any skin response at a patched site will be clinically assessed by a trained blinded evaluator using the scale recommended by the ICDRG, per [Appendix 2](#)

Assessment of the test site areas will be conducted once at baseline (Visit 2/Day 1) prior to any patch (or product) application and then a further 8 times post-baseline during the induction phase, once during the rest phase (for the final induction phase patch removal), and 4 times during the challenge phase (prior to challenge patch application (baseline) and post) by a, trained evaluator who will be blinded to the treatment sequence allocation for both the induction and challenge phases.

During the induction phase; a trained, blinded evaluator will score the test sites for signs of irritation per ICDRG scale ([Appendix 2](#)) at all time points specified in the [study schedule](#). The trained evaluator score will be considered final. The trained evaluator does not need to be medically qualified.

During the challenge phase patch test site assessment will be conducted in a 2-step process:

Step 1: A trained, blinded evaluator will score the test sites for signs of reactions per ICDRG scale ([Appendix 2](#)) at all time points specified in the [study schedule](#). The trained evaluator score will be considered final. The trained evaluator does not need to be medically qualified.

Step 2: For each subject who presents a positive reaction (a score of '+' or greater), a blinded dermatologist will further classify the reaction as potential sensitization (or not) at the final visit and provide a narrative description of the event. The dermatologist will not be scoring the

reaction. A single event may occur over multiple visits. Only one narrative should be made. The narrative must include the start and finish date of the event, a description of how the event evolves over time, any action taken, and diagnosis (potential sensitization reaction, or not, as appropriate). If a clear diagnosis cannot be made, then the dermatologist should include this in the narrative.

If a score (per [Appendix 2](#)) of ‘++’ (Strong) or greater at any point during the induction phase is reported, the next patch will be applied to an adjacent naïve (i.e. previously untreated) site. If a score of ‘++’ (Strong) or greater occurs at the naïve site, no further patch applications will be made. Such reactive subjects will, however, progress to the challenge phase unless, in the opinion of the Investigator (or medically qualified designee), it would be unwise to do so.

The negative control (saline solution) will be used as a reference to contextualise clinical outcomes for the test products by the Sponsor after the study completes and unblinding.

Any cutaneous (dermal) irritation or sensitization reactions which occur within the patch application area and can be completely described by the scale in [Appendix 2](#) will not be recorded as AEs during the study. These responses are typical effects of occluded application of topical products. Reactions to the patch itself or the adhesive will also not be recorded as AEs.

Unexpected or unusual reactions which occur within the patch test area that cannot be completely described by the scale in [Appendix 2](#) (e.g., rash, hives) will be recorded as AEs.

## 4.2 Rationale for Study Design

Compatibility studies represent the first contact of the finished product in humans and seek to demonstrate the safety of topical products under maximised conditions.

The human repeated insult patch test (HRIPT) is a long standing, standard method to determine whether exposure to a topical product will elicit a cutaneous (dermal) irritant or allergic response (sensitization) under exaggerated (occluded) conditions. It is also routinely used and accepted as an appropriate methodology to establish the sensitization potential of topical medicated products by health authorities, including the US FDA and MHRA. The HRIPT requires approximately six weeks and involves three phases: induction, rest and challenge, and is based on the modified Draize test. (Draize *et al*, 1944).

Patch testing techniques and scoring reactions by a grading scale were first standardized in the 1930s. The International Contact Dermatitis Research Group (ICDRG) published the following nonlinear, descriptive grading scale in 1970's (Fregert, 1974) which continues to be widely used and will be adopted for this clinical study ([Appendix 2](#)). A suitable trained (blinded) evaluator will assess the subjects prior and during the induction and challenge phases of the study per the scale in [Appendix 2](#).

The semi occlusive adhesive patch allows an assessment in maximized condition, with adequate contact of the product with the skin and is globally accepted, being widely used in the literature.

Subjects will be assessed by a dermatologist as a prerequisite to enrollment, and again at study end. This study will be conducted under the supervision of a dermatologist.

#### 4.3 Justification for Dose

A critical aspect of a patch test is that the whole test area of the cell is covered with the test product, without spreading or overlapping into other test sites (cells). Previous work has shown that the optimal dose to fulfil these requirements is 0.02 mL/cm^2 (Isaksson *et al*, 2007).

Therefore, in this study each of the test products will be dispensed at a dose of 0.02 mL/cm^2 into individual cells of a semi-occlusive adhesive patch system using an electronic pipette with disposable tips and applied to the designated area on the back. A sodium chloride (NaCl) saline solution (0.9%) will be used as a negative control product and dispensed at the same dose.

The semi-occlusive adhesive patches will be made of a hypoallergenic material and contain round cells of an absorbent material. One of the cells will contain the negative control and 3 other cells will be filled with each the test products according to the supplied randomization allocation for the induction and challenge phase. Only products of the sponsor, GSK CH, will be tested in this study.

#### 4.4 End of Study Definition

A subject will be considered to have completed the study if he or she completes all phases of the study including the last visit or the last scheduled procedure shown in the Schedule of Activities.

The end of this study is defined as the date of the last subject's last visit.

### 5 STUDY POPULATION

#### 5.1 Type and Planned Number of Subjects

Healthy male and female subjects ages 18 to 65, with a Fitzpatrick skin phototype I to IV and no dermatological disorders will be enrolled into this study.

Approximately 470 healthy subjects will be screened to randomize at least 280 subjects to ensure 200 evaluable subjects complete the entire study. If no reaction is observed in 200 subjects, there is a 95% certainty that the actual rate of reaction in the wider population would be less or equal to 1.83%. (Clopper and Pearson, 1934)

An enrolled subject is one who has agreed to participate in the clinical study following completion of the informed consent process directly or via their legally authorized representative and successfully met eligibility criteria to proceed beyond the screening visit.

This study can fulfill its objectives only if appropriate subjects are enrolled. The following eligibility criteria are designed to select subjects for whom participation in the study is considered appropriate. All relevant medical and non-medical conditions should be taken into consideration when deciding whether a subject is suitable for this protocol.

Subject eligibility to participate in the clinical study should be reviewed and documented by an appropriate member of the investigator's study team before subjects are included in the study.

Site personnel assessing the subject inclusion and exclusion criteria and subject eligibility should be the investigator, a suitable qualified medically qualified person or designee as per the needs of the study.

## 5.2 Inclusion Criteria

An individual must meet all of the following inclusion criteria to be eligible for enrollment into the study:

1. Subject provision of a signed and dated informed consent document indicating that the subject has been informed of all pertinent aspects of the study before any assessment is performed.
2. Subject is male or female who, at the time of screening, is between the ages of 18 and 65 years, inclusive.
3. A subject who is willing and able to comply with scheduled visits, treatment plan, and study procedures.
4. A subject in good general and mental health with, in the opinion of the investigator or medically qualified designee, with no clinically significant or relevant abnormalities in medical history or upon dermal examination, or condition, that would impact the subject's safety, wellbeing or the outcome of the study, if they were to participate in the study, or affect the individual's ability to understand and follow study procedures and requirements.
5. Fitzpatrick phototype I to IV (see [Appendix 3](#)).
6. Healthy, intact skin at the proposed test area dorsum (below the shoulder, above the waist), as evaluated by a dermatologist, to ensure subject is free of clinically relevant dermatological conditions.

## 5.3 Exclusion Criteria

An individual who meets any of the following exclusion criteria will not be eligible for enrollment into the study:

1. A subject who is an employee of the investigational site, either directly involved in the conduct of the study or a member of their immediate family; or an employee of the investigational site otherwise supervised by the investigator; or, a GSK CH employee directly involved in the conduct of the study or a member of their immediate family.
2. A subject who has participated in other studies involving investigational product(s) within 30 Days prior to study entry and/or during study participation.
3. A subject who has participated in other studies including non-medicinal, cosmetic studies within 7 Days prior to study entry and/or during study participation.
4. A subject with, in the opinion of the investigator or medically qualified designee, an acute or chronic medical or psychiatric condition or laboratory abnormality that may increase the risk associated with study participation or investigational product administration or may interfere with the interpretation of study results and, in the judgment of the investigator or medically qualified designee, would make the subject inappropriate for entry into this study.
5. A subject who is pregnant or intends to become pregnant during the study duration (self-reported).
6. A subject who is breastfeeding.
7. A subject with known or suspected intolerance or hypersensitivity to the study materials/product (or closely related compounds) or any of their stated ingredients, to hypoallergenic tape, or to the cotton patches.

[figure not shown]
8. A subject who, in the opinion of the investigator or medically qualified designee, should not participate in the study.
9. A subject unwilling or unable to comply with the [Lifestyle Considerations](#) described in this protocol.
10. A subject with current or recent (within last 6 months before the start of the study) history of atopic lesions and/or eczema.
11. A subject with a history of allergic reactions to topical-use products, cosmetics or medications or their ingredients.
12. A subject with any history of significant diseases or medical conditions known to alter skin appearance or physiologic response (e.g. uncontrolled diabetes) which could, in the opinion of the Investigator, preclude topical application of the investigational products and/or interfere with the evaluation of the test site reaction.
13. A subject considered immune-compromised.
14. A subject with active dermatosis (local or disseminated) that might interfere with the results of the study.
15. A subject currently using any medication which in the opinion of the investigator, may affect the evaluation of the investigational product, or place the subject at undue risk.
16. A subject who has used any of the following topical or systemic medications up to two weeks before the screening visit: immuno-suppressants, antihistamines, non-steroidal anti-inflammatory drugs (NSAIDS, high dose aspirin), and/or corticosteroids.
17. A subject who has used a transcutaneous electrical nerve stimulation (TENS) machine 1 day before the screening visit.
18. A subject who has used oral or topical treatment with vitamin A acid and/or its derivatives up to 1 month before the screening visit.
19. A subject who has been vaccinated up to 1 month before the screening visit or is intending to receive a vaccination during their participation in the study.
20. A subject with any skin marks on the back that might interfere with the evaluation of possible skin reactions (e.g. pigmentation disorders, open sores, pimples, cysts, vascular malformations, scars, tattoos, excessive hair, numerous freckles).
21. A subject that intends bathing (in the sea or a pool), using sauna, or partaking in water sports, or activities that lead to intense sweating.
22. A subject that is a prisoner or involuntary incarcerated.
23. A subject from an indigenous tribe.
24. A subject who has previously been enrolled in this study.

#### 5.4 Randomization Criteria

Subjects will be randomized into the study provided they have satisfied all subject selection criteria.

A semi-occlusive adhesive patch with 6 cells labelled A-F will be used. Four cells (A-D) will be used in this study (1 for each test product and 1 for the saline solution). Two cells (E-F) will remain empty.

**Figure 5-1      Example of the semi-occlusive adhesive patch system (shown adhesive side down)**

The sequence of each of the study products to the cells within the patch system for each subject will be randomly assigned per the randomization sequence provided. The sequence of the products to the cells within each subject will remain the same for the induction phase, and a different sequence will be generated for each subject for the challenge phase. For more details on the randomization, please refer to [section 8.1.7](#)

## 5.5      Lifestyle Considerations

During the entire study (Screening – Last Subject Last Visit (LSLV) including the rest phase) the following should be avoided:

- Applying any other product to the test site (dorsum).
- Use of cosmetics, moisturisers, and other topical products on the back area.
- Changing any cosmetic habits, including personal hygiene.
- Changing dietary habits.
- Getting the patch test site wet: during showers or bathing, in pools or lakes/ocean, sauna or activities that cause excessive sweating. The study site will provide instructions on how to shower or bathe throughout the study.
- Removing the patches.
- Wearing tight or restrictive clothing that can remove the patch through friction or cause redness.
- Intentional exposure to artificial ultraviolet (UV) light or cosmetic procedures (includes tanning beds, Intense Pulsed Light, etc.) are prohibited on the test areas for the duration of the study.
- Introduction of new products during the study including but not limited to soap, laundry detergent, or fabric softener.
- Engaging in activities that result in excessive sweating.
- Missing the first day of application during the Induction Phase, or the day of application during the Challenge Phase.
- Missing 2 or more consecutive visits or more than 2 alternate visits.

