## 12 STATISTICAL CONSIDERATIONS AND DATA ANALYSES

### 12.1 Sample Size Determination

Approximately 470 healthy subjects will be screened to randomize at least 280 subjects to ensure 200 evaluable subjects complete the entire study. If no reaction is observed in 200 subjects, the 95% exact confidence interval (Clopper-Pearson method for binomial proportions) for the true rate of positive reactions (in the general population) would be [0, 1.83%]. (Clopper and Pearson, 1934)

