#### 12.2.5 Primary Analysis(es)

The primary analysis will be based on potential sensitization reactions as assessed by a dermatologist and will be conducted on the Safety population.

---

The number and percentage of subjects with any potential sensitization reactions versus those without any potential sensitization reactions will be presented by visit and treatment group.

The 95% exact confidence intervals for binomial proportions using the Clopper-Pearson method (Clopper and Pearson, 1934) will be computed for the proportion of subjects with potential sensitization reactions.

Narrative description of all potential sensitization reactions will be provided.

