1.4 Sample Size Calculation

Approximately 470 healthy subjects will be screened to randomize at least 280 subjects to ensure 200 evaluable subjects complete the entire study. If no reaction is observed in 200 subjects, the 95% exact confidence interval (CI) (Clopper-Pearson method for binomial proportions) for the true rate of positive reactions (in the general population) would be [0, 1.83%].

2 Planned Analyses

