4.1.3 Analysis Populations

The analysis population defined for this study is as follows:

Population	Definition / Criteria	Analyses Evaluated
Randomized	All subjects randomized in induction phase regardless of whether they received study product. Any subject who receives a randomization number will be considered to have been randomized.	Protocol deviations, disposition and medical history listings
Safety	The Safety population will comprise of all randomized subjects who receive any application of the study products.	Primary endpoint, Secondary endpoint, Safety

NOTE:

- To be randomized into the challenge phase, a subject must have been already randomized in the induction phase. Therefore, the randomization status in challenge phase won't be considered to define the randomized population. Only the randomization status in induction phase will be used to define both populations.
- Please refer to [Attachment 1: List of Data Displays](#) which details the population to be used for each of the displays being generated.

This safety study is designed to evaluate cutaneous irritation (local tolerance) and sensitization potential. There are no efficacy outcomes. Therefore, analyses will be conducted only on the Safety population.

Subjects who are randomized in the study, but did not receive any application of the study products, will not be part of safety population. Exclusion of these subjects (if any) from the safety population will be reviewed during the BDRM prior to database lock and approved prior to unblinding. [Listing 16.2.3.1](#) will display the subjects excluded from analysis population of all randomized subjects.

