4.4.1.3 Supportive Analyses

N/A

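### The 1.83% limit rests on 200 evaluable completers, but the primary analysis counts anyone with a single application and has no evaluable set behind it

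*Protocol*

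**What the plan says.** - **Sample size.** Protocol 12.1 plans "to randomize at least 280 subjects to ensure 200 evaluable subjects complete the entire study" and gives [0, 1.83%] as the interval if none of 200 reacts. SAP 1.4 repeats both statements. Neither document says what makes a subject evaluable.
- **Exposure.** Protocol 4.1 plans nine induction applications. Protocol 5.5 and the notes to Table 1-1 list things to avoid: missing the first induction application, missing the challenge application, and "Missing 2 or more consecutive visits or more than 2 alternate visits". These are worded as advice.
- **Analysis set.** SAP 4.1.3 defines the Safety population as "all randomized subjects who receive any application of the study products" and uses it alone for the primary and secondary endpoints. A note there says that challenge-phase randomization plays no part in defining the populations.
- **Primary table.** Under SAP 4.4.1.1 the dermatologist classifies challenge reactions scored '+' or greater as yes, no or unable to determine; the last is not counted as a reaction. Table 14.2.1 then splits the Safety population, by product, into subjects with and without a potential sensitization reaction. Protocol 12.2.5 specifies "The 95% exact confidence intervals for binomial proportions using the Clopper-Pearson method".
- **Support and missing data.** The entry under "4.4.1.3 Supportive Analyses" is N/A. SAP 4.4.3 imputes nothing and keeps dropouts until they discontinue.
- **Stopped induction.** Protocol 4.1 says that after a second '++', at the adjacent naïve site, "no further patch applications will be made". The subject still goes on to challenge unless the investigator thinks it unwise.

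**The concern.** The precision statement and the analysis describe different groups. The first concerns subjects who completed everything and could be judged. The second admits a subject who wore one patch of nine and never returned.

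Protocol section 2 describes sensitization as slow to develop and as typically following repeated exposure. A subject with few induction patches therefore has less chance of reacting at challenge, and one who was never challenged has no challenge reaction to classify. A reactor is counted whatever the exposure, while a little-exposed non-reactor adds only to the denominator. The error therefore runs one way: the rate and its upper limit fall. For a safety endpoint that is the anti-conservative direction, and the upper limit is the number the trial was sized to deliver.

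**Working it through.** **Inputs.** Two-sided 95% Clopper-Pearson interval (Protocol 12.2.5); 200 evaluable and at least 280 randomized (Protocol 12.1, SAP 1.4). The allowance for loss is not stated; it follows as 80/280 = 28.6%. The documents give no rate of missed patches or of subjects never challenged, so the number of extra subjects is taken as a range from 0 to 80.

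**Step 1: reproduce the plan's figure.** With zero events the upper limit is 1 − 0.025^(1/n). For n = 200 it is 1 − 0.025^(1/200) = 1.83%, as stated. The one-sided version, 1 − 0.05^(1/200) = 1.49%, does not match, so the two-sided form is the one the plan uses.

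**Step 2: zero events, larger denominators.**

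| Subjects in denominator | 200 | 220 | 240 | 260 | 280 |
|---|---|---|---|---|---|
| Upper limit | 1.83% | 1.66% | 1.53% | 1.41% | 1.31% |

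**Step 3: a few events.** With x events the upper limit is the 0.975 quantile of Beta(x + 1, n − x).

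| Events | Out of 200: rate (upper limit) | Out of 280: rate (upper limit) |
|---|---|---|
| 1 | 0.50% (2.75%) | 0.36% (1.97%) |
| 2 | 1.00% (3.57%) | 0.71% (2.56%) |
| 3 | 1.50% (4.32%) | 1.07% (3.10%) |

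**Step 4: how far the rate shrinks.** Suppose 80 extra subjects react at a fraction r of the rate in the 200. The expected observed rate is then multiplied by (200 + 80r)/280: 0.71 for r = 0, 240/280 = 0.86 for r = 0.5, and 1 for r = 1. The documents give no value for r, so these are assumptions. The factor 0.71 is the extreme.

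**Step 5: what this does to the interval.** Take the extreme, r = 0: reactions follow Binomial(200, p), but the limit is computed with 280. The chance that the upper limit falls below the true rate p should be at most 2.5%.

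| True rate p | Denominator 200 | Denominator 280 |
|---|---|---|
| 1.31% | 0% | 7.2% |
| 1.83% | 2.5% | 2.5% |
| 2% | 1.8% | 8.9% |
| 3% | 1.6% | 5.9% |
| 5% | 0.9% | 12.4% |

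The error is uneven because the counts are discrete. At four of these five rates it exceeds the nominal maximum.

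**The case against.** Using all exposed subjects is the usual choice for a safety study. Both documents explain it, and SAP 4.4.1.2 plans no formal analysis. That supports keeping the Safety analysis, but not leaving it without a check. Four stronger readings are tempting, and the documents do not support them.

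- **That unchallenged subjects are certainly counted as non-reactors.** This is inferred from the two-way split of the Safety population. SAP 4.4.3 could be read as treating their classification as missing. If so, they leave the denominator. Subjects who were challenged after too few patches stay in, because their challenge data are complete.
- **That a repeated '++' at one cell ends induction for all four products.** The rule speaks of the patch, which carries every product. However, Table 1-1 describes test sites by cell, and no sentence says which unit the stop acts on. If it is the patch, '++' at Visits 3 and 4 would leave every product with 2 of 9 applications. If it is the cell, only the reacting product is affected. No frequency of '++' is given.
- **That the attendance limits have no effect at all.** There are partial controls. Protocol 8.1.7 admits to challenge only subjects who completed induction and remain eligible. Protocol 7.1 allows withdrawal for inability to keep to the visit schedule. Protocol 12.2.2 leaves data exclusions to the blind review, and SAP 4.3.1 has it look at application and adherence deviations. But completing induction is not defined by a number of patches, and the visible text sets no exposure criterion for the review. The only population exclusion that SAP 4.1.3 describes is subjects with no application. The Blind Data Review Plan named in SAP 4.1.2 is not among the documents, so a criterion there cannot be ruled out.
- **That the limit should be raised above 1.83% by removing a further share of the 200.** Dropping 10%, 20% or 30% gives 2.03% (0/180), 2.28% (0/160) or 2.60% (0/140). But the plan already calls those 200 evaluable and randomizes 280 to allow for loss, and nothing in the documents supports these shares. The coherent contrast is 280 against 200.

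It is also fair that Table 14.1.1 will show how many subjects were not randomized to challenge, and that Listing 16.2.5.3 will hold application details. A reader could see the problem there, but would find no rate or interval corrected for it.

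**Conclusion.** The point holds as a gap between what the trial was sized on and what it will report. 'Evaluable' is undefined, the primary set needs one application, challenge reads are not stated as a requirement, and no supportive analysis exists.

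The direction is downward, provided that less induction means less chance of reacting and that Table 14.2.1 uses the whole Safety population as its denominator. Protocol section 2 supports the first condition with the word typically, so it does not show that under-induced subjects cannot react. The second is the natural reading but is not written down.

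The size lies between nothing and the planning extreme: a zero-event limit of 1.31% in place of 1.83%, and rates multiplied by 0.71. Where the trial falls in that range cannot be known from the documents. This should be settled before unblinding. It does not invalidate the Safety analysis.

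**What to change.** 1. In SAP 4.4.1.1, state the denominator of Table 14.2.1 and how subjects without challenge reads are counted.
2. In SAP 4.4.1.3, define before unblinding an evaluable set per subject and product: first induction and challenge applications received, missed visits within the protocol's own limits, and challenge reads available. Add a supportive version of Table 14.2.1 on this set, with exact Clopper-Pearson intervals and the number of the nine induction applications received per product.
3. Keep the Safety analysis, and keep every subject with a potential sensitization reaction in it, whatever the exposure.
4. Report product sites whose induction was stopped for '++' separately, whichever product triggered the stop, and include those never challenged. Keeping only the triggering product in the evaluable set would make inclusion depend on the outcome.
5. Reconcile the passages on the '++' stop so that they say whether it acts on one cell or the whole patch. The clinical rule itself is not judged here.

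The cost is one more table, from application details already planned for Listing 16.2.5.3 and patch-site scores for Listing 16.2.6.2. It brings a second denominator to explain and a slightly wider interval. With 200 evaluable subjects and no events, that interval is the one the plan promised.
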